1.3 Schedule of activities**Table 1–2: Schedule of activities**

| Study period | Evaluation Period | | | | | | Down-Titration Period | Safety Period |
|--|-------------------|------------------------|--|---|--|----------------------|-----------------------|---------------|
| | EV ^a | TC | MEV | FEV | YEV/EDV ^b /EV | UV | | |
| Frequency | | After 2 weeks ± 2 days | Months 3 and 9 during each year of participation | Month 6 during each year of participation | Month 12 during each year of participation (YEV)/ Month 24 or later (FV) | | | |
| Procedures | | | | | | | | |
| Written informed consent | X | | | | | | | |
| Assent form (if applicable) | X | | | | | | | |
| Study participant identification card | X | | | | | | | |
| Inclusion/exclusion criteria | X | | | | | | | |
| Prior and concomitant medications and medical procedures | X | | X | X | X | X | X | X |
| IXRS | X | | X | X | X | X | X | X |
| Recording of AEs | X | X | X | X | X | X | X | X |
| Study drug dispensed | X | X (as applicable) | X | X | X ^d | X (as applicable) | | |
| Study drug returned ^e | | | X | X | X | X (as applicable) | X | |
| Participant diary dispensed | X | | X | X | X ^d | | X | |

| Study period | Evaluation Period | | | | | | Down-Titration Period | Safety Period |
|---|-------------------|----------------------------|--|---|--|----------------|-----------------------|----------------|
| | EV ^a | TC | MEV | FEV | YEV/EDV ^b /FV | UV | | |
| Frequency | | After 2 weeks \pm 2 days | Months 3 and 9 during each year of participation | Month 6 during each year of participation | Month 12 during each year of participation (YEV)/ Month 24 or later (FV) | | | |
| Procedures | | | | | | | | |
| Participant diary retrieved | | | X | X | X | | X | |
| Assessment of childbearing potential | | | X | X | X | | | |
| Complete physical/neurological examination ^f | | | | X | X | | | X |
| Brief physical/neurological examination ^g | | | X | | | X | | |
| Psychiatric and mental status | | | | X | X | | | X |
| Vital signs ^h | | | X | X | X | | X | X |
| Dose adaptation (optional) | | X | X | X | X | X | | |
| Body weight, height | | | X | X | X | | | |
| Laboratory assessments for safety ⁱ | | | X | X | X | | | X ^j |
| BRV plasma concentration ^k | | | | X | X | | | |
| C-SSRS ^l | | | X | X | X | X ^m | X | X |
| EpiTrack Junior ⁿ | | | | X | X | | | X |
| PedsQL ⁿ | | | | X | X | | | |
| ECG ^o | | | | | X | | | X ^j |

| Study period | Evaluation Period | | | | | | Down-Titration Period | Safety Period |
|------------------------------|-------------------|------------------------|--|---|--|-------------------|-----------------------|---------------|
| | EV ^a | TC | MEV | FEV | YEV/EDV ^b /FV | UV | | |
| Frequency | | After 2 weeks ± 2 days | Months 3 and 9 during each year of participation | Month 6 during each year of participation | Month 12 during each year of participation (YEV)/ Month 24 or later (FV) | | | |
| Procedures | | | | | | | | |
| EEG (1h EEG/HV) ^p | | | | X | X | X (as applicable) | | |
| End of study status | | | | X ^q | | | | X |

AE=adverse event; AED=antiepileptic drug; ALP=alkaline phosphatase; ALT=alanine aminotransferase; AST=aspartate aminotransferase; BRV=brivaracetam; C-SSRS=Columbia-Suicide Severity Rating Scale; DTV=Down-Titration Visit; ECG=electrocardiogram; eCRF=electronic case report form; EDV=Early Discontinuation Visit; EEG=electroencephalogram; EV=Entry Visit; FEV=Full Evaluation Visit; FV=Final Visit; GGT=gamma-glutamyltransferase; HV=hyperventilation; IXRS=interactive voice or web response system; MEV=Minimal Evaluation Visit; PedsQL=Pediatric Quality of Life Inventory; PK=pharmacokinetic; S=on-site visit; SAE=serious adverse event; SV=Safety Visit; TC=telephone call; UV=Unscheduled Visit; YEV=Yearly Evaluation Visit

^a The EV is also the last completed study visit of N01269. The following Baseline data will be obtained from N01269 and should not be recorded on the eCRF for this study's EV: demographics, general medical and procedure history, epilepsy history, AED history, seizure count/ absence seizure count, ECG, laboratory assessments for safety, vital signs, body weight, height, physical and neurological examinations, psychiatric and mental status, and recording of epileptic seizures.

^b Participants who discontinue from the study before Month 24 will complete an EDV, unless the participant is transitioning to another BRV study, in which case an FV will be completed (see Section 4.1).

^c Visit should be scheduled at the end of the Down Titration Period. The duration of the Down Titration Period will depend on when the final dose of the study drug was taken during the Evaluation Period, with a maximum duration of 4 weeks. Study participants requiring down titration will complete their daily seizure diaries during the Down-titration Period.

^d No study participant diary will be dispensed at the FV or EDV. Study drug will only be dispensed at the FDV or EDV if the study participant is discontinuing study drug and requires down titration.

^e Drug return includes study drug intake recording and accountability and recording of concomitant AEDs.

^f A complete physical examination will include, at a minimum, general appearance; eyes, ear, nose, and throat; skin; and assessments of the cardiovascular, respiratory, gastrointestinal, and musculoskeletal systems. A complete neurological examination will include, at a minimum, assessments of cranial nerves, motor and sensory systems, deep tendon reflexes, coordination, and gait.

^g A brief physical examination will include, at a minimum, general appearance; assessments of the skin, respiratory system, and cardiovascular systems; and abdomen (liver and spleen). A brief neurological examination will include, at a minimum, assessments of cranial nerves, motor system, coordination, and gait.

^h Vital sign measurements include blood pressure and pulse rate.

ⁱ Full laboratory assessments for safety include hematology and biochemistry (including hepatic monitoring of ALT, AST, ALP, total bilirubin, and GGT) for all study participants and urinalysis for study participants for whom sample collection is feasible. Female study participants of childbearing potential should have a urine pregnancy test done at all laboratory assessment visits. Endocrinology testing will be performed for all study participants <18 years of age at the YEV/FV. For study participants on study drug for more than 12 months, laboratory assessments at MEV can be omitted.

^j At the SV, ECGs and laboratory assessments for safety will be performed only if abnormal at the EDV or FV.

^k At the FEV and YEV/EDV/FV Visits, when PK sampling is planned, study participants should not take their morning BRV dose prior to arriving in the clinic.

^l The C-SSRS will be completed by study participants ≥ 6 years of age. The “Since Last Visit” version of the C-SSRS will be used, with the following exception: If study participant turns 6 years of age during EP0132, the “Already Enrolled” version of the C-SSRS should be completed at the first visit after the sixth birthday, and the “Since Last Visit” version of the C-SSRS should be completed at subsequent visits.

^m If an Unscheduled Visit is needed, the assessments noted will be performed. Additional assessments can be performed at the Investigator’s discretion. If an unscheduled visit is conducted due to safety or efficacy reasons, the C-SSRS will be performed for study participants ≥ 6 year of age.

ⁿ Additional details for the patient-reported outcomes (ie, versions and ages) are provided in Table 8–1.

^o An ECG must be scheduled once a year at the YEV and at the EDV in the case of early discontinuation.

^p The investigator/designated EEG reader should attempt to keep the study participant awake for the duration of the 1-hour EEG; a minimum of 30 minutes of awake time will be required for evaluability.

^q End of study status only for study participants who continue in the study until it ends (SV) and for whom the visit corresponds to the FV.

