7.3.2 Seizure diary

During the study, study participants will keep a diary to record daily seizure activity from the EV until the EDV or FV (as applicable). Study participants who discontinue study drug and require down titration will also complete their daily seizure diaries during the Down-titration Period. Study participants will be reminded to bring their diary with them to each clinic visit.

The written information is discussed with the study participants at each visit in order to ensure completeness and accuracy. As a result of the discussion, the Investigator will assess and confirm the seizures according to the ILAE codes and record the seizure types in the eCRF/diary; he/she will also confirm the presence of AEs, if applicable.

Study participants will record all types of seizures that occur in their diaries and will be educated to complete their diary entries after each seizure or at least once a day. A parent or caregiver may assist in completing the diary if necessary.

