To investigate the long-term safety and tolerability of BRV in pediatric study participants with CAE or JAE	
TEAEs requiring a change in BRV doseMaximum intensity TEAE experienced (mild, moderate, and severe)Drug-related serious TEAEsFatal adverse events (AEs)TEAEs by maximum relationship (related and not related to BRV)SAEs by maximum relationship (related and not related to BRV) 
Occurrence of other seizure types, including generalized tonic-clonic seizures (GTCS), based on diary or EEG:
 
Non-absence seizures based on 1-hour EEGNon-absence seizures based on diary 
Estimand: the estimand is defined by the following 4 attributes that will be used to define the treatment effect of interest for the other safety analysis:
 
Population: population as defined in the protocol-specified inclusion/exclusion criteria reflecting the target patient population who receive at least 1 dose BRV during the study.Study participant-level outcome: occurrence of events in the list of endpoints above.Intercurrent event handling: the intercurrent event of concomitant medication use is handled by using a treatment policy strategy in which all AE/TEAE data or seizure data (as applicable) are included, regardless of receipt of any concomitant medication.Population-level summary measure: incidence rates. 
The intercurrent event of treatment discontinuation is handled by using a while-on-treatment strategy where observation ends at 14 days after treatment is stopped.

To investigate the long-term safety and tolerability of BRV in pediatric study participants with CAE or JAE	
CFB to each applicable visit in safety laboratory testsCFB to each applicable visit in electrocardiogram (ECG) parametersECG findings at each applicable visit

Table 2-1: Primary objective

Objectives	Endpoints/estimands
	
Physical and neurological examinations findings at each applicable visitPsychiatric and mental status at each applicable visitCFB to each applicable visit in vital signs (blood pressure, pulse rate, body temperature)CFB to each applicable visit in body weight and height

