2.3.3.2 Daily seizure diaries

Data from daily seizure diaries will be collected during the Evaluation Period (from the EV until the EDV or FV as applicable) and the Down-Titration Period for participants who down-titrate. Study participants will record all types of seizures that occur in their diaries and will complete the diaries after each seizure or at least once a day.

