10.5.2 Non-absence seizure incidence during the study based on seizure diary

The incidence of each non-absence seizures type observed from the seizure diary will be summarized over the entire Evaluation Period (including unscheduled visits and visits beyond Month 24) and by 3-month period, as defined in [Table 3-3](#); 3-month periods from and beyond Months 25-27 will be included if at least one participant has started the relevant 3-month period. Study participants who experience more than one non-absence seizure type during a 3-month period (ie, POS and tonic-clonic, POS and other seizure, tonic-clonic and other seizure or all three seizure types) will be counted once for each non-absence seizure type. Percentages for the

each 3-month period will be relative to the number of participants who completed their seizure diary on at least 80% of days within the 3-month period. Percentages for the Evaluation Period will be relative to the number of participants who completed their seizure diary on at least 80% of days over the Evaluation Period.

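### The schedule supplies no seizure diary for down-titration although daily diaries are required then, and the SAP's diary summary of non-absence seizures ends before the estimand's observation window does.

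*Protocol*

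**What the plan says.** **Diaries are required during down-titration.** Footnote c of Protocol Table 1-2: "Study participants requiring down titration will complete their daily seizure diaries during the Down-titration Period". Protocol 7.3.2 says the same: "Study participants who discontinue study drug and require down titration will also complete their daily seizure diaries during the Down-titration Period". SAP 2.3.3.2 plans diary data for the Evaluation Period "and the Down-Titration Period for participants who down-titrate".

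**Diaries are not supplied for it.** The row "Participant diary retrieved" is marked at the combined YEV/EDV/FV column, so the current diary is handed in there. Footnote d says of the same visits: "No study participant diary will be dispensed at the FV or EDV". That footnote makes an exception for study drug, "if the study participant is discontinuing study drug and requires down titration", but none for the diary. The dispensing and retrieval rows are both marked once more, in the Down-Titration column. Neither is marked in the Safety Period column.

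**What is estimated and what is summarised.** Non-absence seizures by diary and by EEG are endpoints under the primary safety objective. Their estimand handles treatment discontinuation with a "while-on-treatment strategy where observation ends at 14 days after treatment is stopped" (SAP Table 2-1; Protocol Section 3 has the same rule). SAP 10.5.2 says the diary incidence "will be summarized over the entire Evaluation Period (including unscheduled visits and visits beyond Month 24) and by 3-month period". SAP 3.3.2 ends the Evaluation Period at the FV or EDV.

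**The concern.** There are two faults, and correcting one does not correct the other.

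The first is operational. Following the schedule to the letter, a site sends the participant home with tapering supplies and no diary. It then issues a diary at a visit where the period to be recorded is already over. The schedule also expects a diary back at that visit which it never provided.

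The second is analytical. The estimand's observation runs through the taper and for two weeks beyond it, but the diary table stops at the FV/EDV. Even if every participant kept a perfect diary during the taper, none of those entries would reach a summary.

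At stake is the diary-based incidence of non-absence seizures, including generalized tonic-clonic seizures, over a stretch for which the protocol itself chose to require daily recording.

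**Working it through.** The documents give no figure on this point and no sample size calculation, so the check is a comparison of passages plus day counts.

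**1. Can the Down-Titration column supply the diary?** Protocol Table 1-1 shows one visit in that period, the Down-Titration Visit (DTV). Footnote c and Protocol 4.1 place it at the end of the period, and Protocol 4.1 has study drug discontinued there. The other marks in the column fit this reading: study drug is returned there and not dispensed. A diary issued at the DTV cannot cover the preceding weeks, and no later retrieval is scheduled. So it cannot.

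**2. Is there another supply route?** The only written fallback for recording seizures without a new diary is in Protocol 4.1.1, for participants who cannot return to the clinic because of COVID-19.

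**3. Is there another seizure instrument?** Protocol 7.3.1 schedules no EEG after the FV/EDV.

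**4. Length of the gaps.** Inputs: taper of at most 4 weeks (Protocol 4.1); estimand end at 14 days after the last dose; summary end at the FV/EDV.

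- Diary gap = 7 × taper weeks.
- Window gap = 7 × taper weeks + 14.

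| Taper | Days without a supplied diary | Days from FV/EDV to end of estimand observation |
|---|---|---|
| None (SAP 2.3.1: already at the lowest level) | 0 | 14 |
| 1 week | 7 | 21 |
| 2 weeks | 14 | 28 |
| 4 weeks (maximum) | 28 | 42 |

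**5. Share of follow-up for a full-length taper.** Visit days are from SAP Table 3-5.

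- FV at Month 24 (day 731): 28/(731 + 28) = 28/759 = 3.7%; 42/(731 + 42) = 42/773 = 5.4%.
- EDV at Month 6 (day 183): 28/(183 + 28) = 28/211 = 13.3%; 42/(183 + 42) = 42/225 = 18.7%.

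**6. How far a diary at the FV/EDV would go.** It would cover at most 28 of the 42 days, 28/42 = 67%. The last 14 days have neither diary nor EEG planned, so the estimand text still needs reconciling.

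**7. Comparison with the adverse event tables.** SAP 10.2 applies the 14-day window explicitly to treatment-emergent adverse events, except those leading to permanent discontinuation. SAP 10.5.1 and 10.5.2 contain no equivalent for non-absence seizures.

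**The case against.** The strongest reply is that little is lost in practice.

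- **Adverse events are still recorded** at the DTV and the Safety Visit, and summarised to 14 days after the last dose. Protocol Appendix 3 names convulsions without hospitalization as an example of an important medical event, and Table 8-2 lists convulsion and status epilepticus among anticipated serious events that must still be reported. A reader might infer that seizures during withdrawal go unrecorded; the documents do not support that. The reply is incomplete, though. Appendix 3 also excludes expected signs of the studied disease unless they are more severe than expected, and diary non-absence seizures are a separate endpoint.
- **The intention is clear.** Footnote c, 7.3.2 and the retrieval mark in the Down-Titration column all presume a diary in hand, and a site may act on those instead of footnote d. This stands: it is an inconsistent dispensing instruction, not a plan without diaries, and 28 days is a ceiling, not a forecast.
- **Down-titration entries are listed** (Protocol 9.3.1, SAP Section 8). True, but a listing gives no incidence.
- **The SAP window is in line with Protocol 9.4.1**, which plans non-absence summaries by scheduled visit. That explains the window but does not align it with the estimand.
- **The column heading is partly lost** in the available copy, so assigning its marks to the DTV is an inference. Table 1-1, footnote c and the drug-return mark all support it.

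**Conclusion.** The passages on diary supply contradict one another and must be reconciled. Under footnote d, a participant who down-titrates has no supplied diary for up to 28 days. Separately, the diary summary of non-absence seizures closes up to 42 days before the estimand's stated end of observation, and 14 days before it for someone who stops without a taper.

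Two stronger readings should be resisted. A reader might infer that footnote d makes the estimand unattainable. It does not do so alone: the SAP window and the absence of any instrument in the final 14 days would leave the mismatch in place even with a diary supplied. A reader might also infer that reported incidence is biased downward for everyone who stops brivaracetam. That is not shown. An incidence labelled as covering the Evaluation Period is not biased for that period, participants already at the lowest level have no taper, and the documents give no rate of seizures on withdrawal. What remains is a risk of under-counting against the estimand's own window.

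Absence seizure freedom endpoints are unaffected, since the SAP confines them to the Evaluation Period up to Month 24. The number affected cannot be computed. It excludes participants who move to another brivaracetam study, an access program or commercial supply. The maximum figures assume a 4-week taper, and the diary gap assumes that the site follows footnote d.

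**What to change.** **Protocol.** Amend footnote d so that a diary is dispensed at the FV/EDV when the participant will down-titrate. Keep the existing retrieval mark at the DTV and remove the dispensing mark there.

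**SAP 10.5.2.** Add two rows:

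- diary non-absence seizures in the Down-Titration Period, with participants entering that period as denominator and the number having diary data shown beside it;
- an overall row running to the end of diary recording.

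**Estimand text (Protocol Section 3, SAP Table 2-1).** State that seizure-diary observation ends with diary recording, and that seizures in the following 14 days, for which no diary or EEG is scheduled, are captured only as adverse events.

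**Cost.** One footnote, one table cell, two SAP table rows and a sentence in the estimand, plus one extra diary per down-titrating participant. No visit is added and dosing is untouched. If the protocol can no longer be amended, the SAP rows and a plain statement of how many tapering participants had diary data are still worth having.

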10.3 Clinical laboratory evaluations

10.3.1 Hematology, Clinical chemistry, Endocrinology and Urinalysis parameters

Hematology, clinical chemistry, and urinalysis variables are assessed at MEV, FEV, YEV, FV, and EDV, and will also be assessed at SV if abnormal at the FV or EDV. For study participants on study drug for more than 12 months, laboratory assessments at MEV can be omitted.

Endocrinology variables are assessed at the YEV/FV for study participants aged <18 years.

Observed results as well as CFB will be summarized descriptively, by visit, for all laboratory variables.

The definition of PCS is described in [Section 3.4](#). The criteria for a laboratory value to be PCS are defined in [Section 13.1.1](#) and [Section 13.1.2](#). All laboratory measurements will be assessed to determine if they meet PCS criteria. The number and percentage of study participants with PCST values for each laboratory variable (ie, PCST low value, PCST high value) for hematology, biochemistry, endocrinology and urinalysis will be summarized, over all visits (including unscheduled visits) and by visit separately. Percentages in the overall summary will be relative to the number of study participants with at least one assessment on or after the first dose of BRV in EP0132. Percentages in the by visit summary will be relative to the number of study participants with a measurement at the visit. Note that the urinalysis variables nitrites, pH, and specific gravity will not be assessed against PCS criteria and thus will be listed only.

For female participants of childbearing potential, a urine pregnancy test is performed at MEV, FEV, YEV, FV or EDV as applicable, and SV. A urine pregnancy test may also be performed at unscheduled visits. Serum pregnancy tests are performed for PDILI assessments and local laboratory assessments. Pregnancy test results will not be summarized.

Summaries of laboratory variables will only summarize variables planned per the protocol, however, both planned and unplanned laboratory variables will be provided in data listings. Unscheduled laboratory tests conducted by local laboratories are unplanned so will be included in the listings only.

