10.4.2 Electrocardiograms

ECGs are performed at YEVs, EDV or FV (as applicable), and SV.

Observed values and CFB for each measurement will be summarized at each scheduled visit.

Summaries of shift from N01269 Baseline to each visit will be provided based on the categories normal, abnormal (not clinically significant) and abnormal (clinically significant). Percentages will be relative to the number of study participants with a measurement at the visit.

The observed values and CFB values for the QTcB parameter will be presented descriptively. The definition of PCS is described in [Section 3.4](#). ECG PCS criteria are located in [Section 13.1.4](#). All QTcB measurements (scheduled and unscheduled) will be assessed to determine if they meet PCS criteria. The number and percentage of study participants that meet the criteria for PCST will be presented for QTcB by visit.

QTcB data and findings will be listed by study participant and visit.

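### Safety Visit ECGs and laboratory tests are taken only from participants abnormal at the EDV/FV, so by-visit percentages of those measured are not comparable with the on-drug visits

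*Protocol*

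**What the plan says.** The SV follows two weeks off study drug (Protocol 4.1). Protocol Table 1-2 marks both the ECG and the safety laboratory cells at that visit with footnote j: "At the SV, ECGs and laboratory assessments for safety will be performed only if abnormal at the EDV or FV".

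SAP 10.3.1 carries the condition over for laboratory tests, which "will also be assessed at SV if abnormal at the FV or EDV". SAP 10.4.2 does not carry it over for ECGs: "ECGs are performed at YEVs, EDV or FV (as applicable), and SV".

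The summaries are specified as follows.

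- **Laboratory (SAP 10.3.1):** observed values, change from Baseline (CFB) and PCST counts by visit. For PCST, "Percentages in the by visit summary will be relative to the number of study participants with a measurement at the visit".
- **ECG shift (SAP 10.4.2):** "Summaries of shift from N01269 Baseline to each visit will be provided", in three categories (normal, and abnormal with or without clinical significance). "Percentages will be relative to the number of study participants with a measurement at the visit".
- **QTcB (SAP 10.4.2):** "PCST will be presented for QTcB by visit". No denominator is given, so the SAP 3.2 default applies, which is participants with at least one assessment at the time point.

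Under SAP 3.4 a value counts as PCST even if the participant had met the criteria before, so a persisting abnormality counts again at the SV. Neither section removes the SV, changes its denominator or mentions the selection.

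**The concern.** At the YEV, EDV or FV an ECG is due from everyone attending, and the percentage abnormal estimates a prevalence on drug. At the SV it is due only from those abnormal at the EDV or FV. A percentage of those measured then answers a different question: of the participants who were abnormal, how many still are? Printed next to the on-drug columns under the same heading, it looks like an off-drug prevalence.

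The SV is the only off-drug visit, so its column is where a reader would look to see whether abnormalities clear after brivaracetam is stopped. By-visit means and CFB at the SV would carry the same selection. ECG findings and changes in laboratory and ECG parameters at each applicable visit are listed endpoints under the primary safety objective (SAP Table 3-1), so these tables will be read.

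**Working it through.** The plan states no abnormality rate for the SV or the EDV/FV, so there is no figure to reproduce. All rates below are assumptions, shown as ranges.

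**Definitions**

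- p = share abnormal at the EDV/FV: 5%, 10%, 20%
- r = share of those still abnormal at the SV: 30%, 50%, 70%
- q = share newly abnormal at the SV among those normal at the EDV/FV: 2%, 5%

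**ECG shift table.** The retest trigger and the tabulated outcome are essentially the same variable.

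- Shown by the planned SV row: r
- Shown if every SV attendee were tested: p × r + (1 − p) × q
- Ratio: r / [p × r + (1 − p) × q], which exceeds 1 whenever r > q

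| p | r | q | Planned SV row | If all were tested | Ratio |
|---|---|---|---|---|---|
| 5% | 70% | 2% | 70% | 3.5% + 1.9% = 5.4% | 13.0 |
| 5% | 30% | 2% | 30% | 1.5% + 1.9% = 3.4% | 8.8 |
| 10% | 50% | 2% | 50% | 5.0% + 1.8% = 6.8% | 7.4 |
| 5% | 50% | 5% | 50% | 2.5% + 4.75% = 7.25% | 6.9 |
| 20% | 30% | 5% | 30% | 6.0% + 4.0% = 10.0% | 3.0 |

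Over the whole grid the planned row reads 30-70%, against 3.4-18.0% if all were tested. The ratio runs from 3.0 to 13.0.

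**Direction of the true change.** Compare p with the all-tested rate. It falls from 10% to 6.8% in the third row and from 5% to 3.4% in the second. It rises from 5% to 7.25% in the fourth and from 5% to 5.4% in the first. The assumptions do not fix the direction.

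**Size of the SV denominator.** If all of the approximately 140 planned participants attended and p = 10%, the SV row would rest on 140 × 0.10 = 14 people. With an assumed 60 attending it would rest on 6. Participants who move to another brivaracetam source have no SV (Protocol 4.1), so attendance will be below the full enrolment.

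**Laboratory PCST.** The persistence formula does not carry over directly, because the trigger is an undefined abnormality while the outcome is a separate threshold for each analyte (for AST, above 180 or 144 U/L by age, SAP Table 13-1). A general bound still holds: the ratio cannot exceed 1 / (share retested). The documents do not say whether one flag brings back one test or the whole panel. For a full panel of k independent analytes, each flagged with probability a, the share retested is 1 − (1 − a)^k.

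- k = 15, a = 1%: 14% retested, ratio at most 7.15
- k = 30, a = 5%: 79% retested, ratio at most 1.27

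**QTcB PCST.** The trigger is any ECG abnormality and the outcome is a QTcB limit (SAP Table 13-6). The SV percentage is therefore selected, but it is not simply a persistence rate.

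**The case against.** The strongest objection is that no text names an SV column. SAP 10.4.2 summarizes ECG values and CFB at scheduled visits, Protocol 9.4.1 does the same for laboratory data, and SAP Table 3-5 lists only MEV, FEV and YEV as scheduled assessment visits. For ECG values and CFB this is a fair reading. It does not reach the ECG shift to each visit, the QTcB PCST by visit or the laboratory summaries by visit in SAP 10.3.1, and SAP 10.4.2 itself names the SV as an ECG visit. Where the SAP means to leave the SV out it restricts the visits: the neurological and psychiatric shift tables (SAP 10.4.4 and 10.4.5) name only FEV, YEV and FV. The column is implied, not stated.

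Second, no row for the last on-drug visit is planned beside the SV. FVs are mapped to scheduled visits, and EDVs outside a window are not mapped (SAP 3.3.7 and 3.3.8). That stands. The misreading would come from comparing the SV with the on-drug columns generally.

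Third, the analysis is descriptive, the counts would show a small SV group, data are listed, and clinically significant findings are also captured as AEs. All true, and it limits the consequence. But a small count signals imprecision; it does not tell the reader that everyone in it was chosen for being abnormal.

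Two stronger readings are tempting. A reader might infer a 20-fold overstatement: with p = 5% and r = 50%, 50% against 5% × 50% = 2.5%. That counts every untested participant as normal, which the documents do not support. A reader might also infer that the table reverses the true direction of change. That too needs almost no new off-drug abnormalities, and the working shows plausible inputs for which the true rate rises.

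**Conclusion.** The point holds as a denominator problem at one visit. Followed as written, the plan gives SV percentages conditional on an earlier abnormality, and they should not be read against the on-drug visits.

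For the ECG shift table the overstatement is about 3 to 13 times under the assumed ranges, and it requires persistence to exceed new onset (r > q). That is expected but not guaranteed. If abnormalities cleared almost completely off drug, the SV row would not be inflated. New abnormalities in participants normal at the EDV/FV would go unseen in either case. For laboratory and QTcB PCST the inflation is smaller and its size uncertain, because the trigger differs from the PCS threshold and may bring back a whole panel.

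The true direction of change from on to off drug is unknown. The primary TEAE endpoints do not use this denominator. The over-all-visits laboratory PCST summary counts everyone assessed on or after first dose and is also unaffected. Nothing is tested formally. This is a cheap correction to how one visit is presented, and it does not threaten the main safety conclusions.

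**What to change.** 1. In SAP 10.3.1 and 10.4.2, state that the SV is excluded from the by-visit value, CFB, ECG shift and PCST summaries.
2. Add one table that reports SV results as resolved or persisting among participants abnormal at the EDV/FV, with that number as the stated denominator. Include QTcB PCST in it, since SAP 10.4.2 plans QTcB PCST by visit only and gives no over-all-visits summary that would otherwise hold those results.
3. Reconcile the SAP 10.4.2 sentence on SV ECGs with Protocol Table 1-2 footnote j.
4. Keep SV data in the over-all-visits laboratory PCST counts and in all listings.

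The cost is a few lines of SAP text and one small extra table. No new data are needed and study conduct does not change.
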